8.5.2 Secondary Outcome Measure

8.5.2.1 Sheehan Disability Scale (SDS) for PTSD for MAPS

The SDS is a 5-item measure of functional impairment [115]. The items indicate degree of impairment in the domains of work/school, social life, and home life, with response options based on a 10-point scale (0=not at all to 10=extremely), and five verbal tags (not at all, mildly, moderately, markedly, extremely). The SDS has high internal consistency and accurately identified 80% of a sample of primary care patients with mental disorders [116]. The Customized version of the SDS for PTSD for MAPS was developed utilizing the standard SDS. The first three items indicate degree of impairment in the domains of work/school, social life, and home life, with response options based on a 10-point scale (0=not at all to 10=extremely), and five verbal tags (not at all, mildly, moderately, markedly, extremely). The remaining two items assess Days Lost and Days Unproductive during the reporting period. The SDS for PTSD for MAPS maintains the same scale conventions as the standard SDS. To limit missing data, the summary measure used to analyze the treatment effect on SDS is the mean of the 3 item responses at each visit. Any participant who did not work during the reporting period due to reasons related to PTSD is scored as maximal work-related impairment on item 1. Any participant who did not work during the reporting period due to reasons not related to PTSD reports on the reason for not working and Item 1 is skipped. The SDS for PTSD for MAPS has been approved by [name] for use in MAPS Research and is referred to throughout the protocol as SDS. The SDS for PTSD for the MAPS takes approximately 5 minutes to complete.

To limit missing data and ensure standardized administration, the SDS for PTSD for MAPS will be administered in a clinician-rated format by the centralized IR Pool via Teleassessment.

8.5.3 Screening Measures and Reliability

8.5.3.1 Mini-International Neuropsychiatric Interview (MINI)

This version of the MINI (7.0.2), a structured interview that was first developed in 1998 to be compatible with DSM and International Classification of Disease (ICD) criteria for psychiatric illnesses [117]. It is now compatible with DSM-5 and will be administered to screen for all major psychiatric conditions other than personality disorders. Each module of the MINI consists of two or three questions where the answer is either “Yes” or “No,” and decision-tree logic is used to determine whether to ask additional questions [118]. MINI items were highly reliable (interrater reliability between kappa of 0.8 and 0.99, test-retest reliability between 0.6 and 0.9 for all scales save “current mania”), and diagnosis via MINI was comparable to that made with the Composite

Diagnostic Interview and the SCID [119, 120] Testing on non-psychiatric samples did not create false positives [117]. The MINI takes approximately 90 minutes to complete.

To limit missing data and ensure standardized administration, the MINI will be administered in a clinician-rated format by the centralized IR Pool via Tele-assessment.

8.5.3.2 Structured Clinical Interview for DSM-5 for Personality Disorders: Self-report Questionnaire (SCID-5-SPQ)

The SCID-5-SPQ is a brief questionnaire designed as a self-report screening tool used to assess for personality disorders [121]. Potential personality disorders that satisfy diagnostic thresholds will be further assessed via clinical interview during the SCID-5-PD, see below. The SCID-5-SPQ takes approximately 20 minutes to complete.

8.5.3.3 Structured Clinical Interview for DSM-5 for Personality Disorders (SCID-5-PD)

The SCID-5-PD is a semi-structured diagnostic interview that assesses the 10 personality disorders of the DSM-5 [121]. The clinical interview is informed by answers on the self-reported questionnaire (SCID-5-SPQ). The SCID-5-PD takes approximately 60 minutes to complete.

To limit missing data and ensure standardized administration, the SCID-5-PD will be administered in a clinician-rated format by the centralized IR Pool via Tele-assessment.

8.5.3.4 Life Events Checklist for DSM-5 (LEC-5)

The LEC-5 is a 17-item self-report instrument designed to determine the presence of traumatic life events in the assessment and diagnosis of PTSD. It is a companion measure to the PCL-5 and will be used to assess PTSD. The participant indicates whether each event listed has occurred during their lifetime, permitting the possibility of marking multiple events [122]. The LEC-5 takes approximately 5 minutes to complete.

8.5.3.5 PTSD Checklist for DSM-5 (PCL-5)

The PCL-5 is a 20-item self-report questionnaire in which respondents indicate the presence and severity of PTSD symptoms, derived from the symptoms of PTSD per DSM-5 [123]. Participants indicate how much distress they have experienced due to symptoms such as "Repeated, disturbing memories, thoughts, or images of a stressful experience from the past," "Trouble remembering important parts of a stressful experience from the past," and "Feeling irritable or having angry outbursts" on a 5-point Likert-type scale (1=Not at all to 5=Extremely). The PCL-5 takes approximately 8 minutes to complete.

8.5.3.6 Dissociative Disorders Interview Schedule for DSM-5 (DDIS)

Questions on the DDIS specifically addressing dissociative disorder symptoms will be administered by a blinded IR via telemedicine. These questions are part of an intensive interview that includes questions concerning somatic and psychiatric symptoms. The interview is intended to assess and potentially distinguish between dissociative disorders and other disorders and between Dissociative Identity Disorder (DID) and a dissociative disorder not otherwise specified [124]. Owing to overlap with items found between the DDIS and other screening measures, only questions specifically addressing DID (items 117 to 132) will be assessed. The DDIS takes approximately 5 minutes to complete.

To limit missing data and ensure standardized administration, the DDIS will be administered in a clinician-rated format by the centralized IR Pool via Tele-assessment.

8.5.4 Exploratory Measures

8.5.4.1 DSP-I (The Dissociative Subtype of PTSD Interview)

The DSP-I is a clinician-administered interview designed by an international team of PTSD researchers to detect and assess severity of the dissociative type of PTSD [125]. It is recommended for use as an additional or complementary measure (“add-on”) to the CAPS-5. Assessments of military veterans and civilians support the existence of a dissociative subtype of PTSD that is associated with PTSD severity and derealization and depersonalization [126-128]. It consists of two parts, but only Part 1 will be administered. Part 1 contains five items addressing depersonalization, four items addressing derealization, and a section that is administered if dissociative episodes are endorsed that assesses duration and perceived cause of episodes (seven items) and observer items (three items) addressing interviewee demeanor, including evidence of dissociation, such as forgetfulness or giving a statement that is bizarre within the context of the interview. If two or more items within this section are endorsed, this indicates the presence of other dissociative symptoms beyond depersonalization and derealization. The DSP-I takes approximately 15 minutes to complete.

To limit missing data and ensure standardized administration, the DSP-I will be administered in a clinician-rated format by the centralized IR Pool via Tele-assessment.

8.5.4.2 Adverse Childhood Experience Questionnaire (ACE)

The ACE is a 10-item checklist measure assessing number and types of adverse childhood experiences, including neglect and emotional, physical, and sexual abuse. The measure was first used in the context of a study investigating the relationship between childhood adverse experiences and health outcomes in adulthood [129]. Respondents are asked if an experience happened “often” and if so, to write “1”. The total score reflects the number of adverse childhood experiences. Number of frequent adverse childhood experiences is associated with adverse health outcomes in adulthood, including greater likelihood of heart disease, chronic pain, and poor work performance [130-133]. The scoring method has been used in archival research, finding an association between increased scores and health problems in several generations [132]. In addition, developmental trauma events (DTE) during childhood and adolescence, including description and frequency of the events will be evaluated at screening and throughout the trial. The ACE takes approximately 4 minutes to complete.

8.5.4.3 Group Questionnaire (GQ)

The GQ is a 30-item self-report measure of the quality of the therapeutic relationships in a group setting. The GQ is empirically validated and sensitive to group level processes [134] with acceptable correlations with the Working Alliance Inventory, the standard measure of therapeutic alliance in individual therapy [135]. Subscales assess Positive Bonding (13 items), Positive Work (8 items), and Negative Relationships (9 items) organized within three structural dimensions: member-member, member-group, and member-leader relationships. Questions are rated on a 7-point Likert-type scale, 1 (not true at all) to 7 (very true). The measure yields a score for each of the three subscales, which have good internal consistency [134-136]. The GQ takes approximately 10 minutes to complete.

8.5.4.4 Beck Depression Inventory II (BDI-II)

The BDI-II is a revision of the BDI, a 21-item self-report measure [137, 138] that will serve as a measure of depression symptom severity [139]. The BDI-II has been validated, has high internal consistency and good test/re-test reliability, and is not overly sensitive to daily variations in mood [139]. Score cutoffs indicate: 0 to 13 minimal depression, 14 to 19 mild depression, 20 to 28 moderate depression, and 29 to 63 severe depression. Initial and subsequent studies report that the BDI-II total score has a reliability coefficient of 0.90 to 0.91 which is related to other measures of depression symptoms [140, 141]. The BDI-II takes approximately 10 minutes to complete.

8.5.4.5 Experiences in Close Relationships-Short Form (ECR-S)

The ECR-S is a 12-item self-report measure of the construct of adult attachment, resulting in scores for two factors: attachment anxiety and attachment avoidance. Questions are rated on a 7-point Likert-type scale. For this study, the term “romantic” will be substituted for “intimate,” defined as “emotional closeness, including close family relationships and/or romantic relationships”. Brennan et al. (1998) reported that the ECR long version had a high level of internal consistency within the two factors, with coefficient alphas of 0.91 and 0.94 for the Anxiety and Avoidance subscales, respectively [142]. This was confirmed for the short version of the scale with coefficient alphas of 0.78 (Anxiety) and 0.84 (Avoidance) [143]. Correlations between the Anxiety and Avoidance subscales were low ($r=0.19$), which indicates that these two subscales reflect distinct dimensions of attachment. The ECR-S also possesses good test-retest reliability and construct validity. The ECR-S takes approximately 5 minutes to complete.

8.5.4.6 Posttraumatic Growth Inventory (PTGI)

The PTGI is a 21-item scale assessing positive outcomes following trauma. The scale includes factors of New Possibilities, Relating to Others, Personal Strength, Spiritual Change, and Appreciation of Life. The PTGI is modestly associated with personality traits of optimism and extraversion. The scale has been used to assess how individuals have reconstructed or strengthened their perceptions of self, others, and the meaning of events in the aftermath of trauma [144]. The PTGI takes approximately 5 minutes to complete.

8.5.4.7 Cornell Services Index (CSI)

The CSI was developed to document the quantity and type of services used by adults seeking mental health treatment in Westchester County, New York, as part of an NIMH-funded study. Among the virtues of this instrument are its inclusion of all types of services (except pharmacy) while including a special focus on mental health services and ease of administration and portability. The CSI Guidelines for Administration and Scoring provides instructions on how a

trained interviewer would elicit accurate information to complete the form. Raters are taught to help interviewees establish the reference period by using holidays or personal events to define the assessment period. The validated assessment period is 3 months. The CSI's interrater and test reliability were evaluated in a sampled of 40 adults who sought mental health treatment [145]. Interclass correlation coefficient for all service types was 0.98, and test-retest reliability ranged from 0.54 to 1.00 which was deemed moderate to high. This protocol will utilize a modified version of the CSI in which all services are recalled for 6 months to balance the accuracy of self-report for outpatient visits and inpatient stays. This reference window would also better allow a pre-study/post-study comparison with the schedule of assessments because having more time for health service utilization would improve the duration over which we can expect to capture both outpatient and inpatient health services. The likelihood of detecting a relatively rare event of going to the hospital is greater over a 6-month period vs. a 3-month period. The CSI takes approximately 3 minutes to complete.

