Assess incidence of AESIs, defined as AEs specified in the protocol related to cardiac function, suicidality, and abuse liability.	All visits following enrollment	AEs reported in eCRF
Assess incidence of SAEs.	All visits	SAEs reported in eCRF
Assess incidence of psychiatric concomitant medications taken.	Phone and Site Screening, all visits with exception of Preparatory Session 1 and (Outcome)	Medication review
Assess relative incidence of positive or serious ideation and suicidal behavior.	All site visits	C-SSRS
Assess mean changes in physiological measures.	Site Screening, Experimental Session 1 and Experimental Session 2 (pre-IMP administration and end of visit)	Blood pressure, heart rate, and body temperature
Exploratory		
Evaluate group cohesion within and between cohorts based on comparison of PTSD treatment outcome.	CAPS-5 (Baseline) and (Outcome)	CAPS-5
Assess changes in severity of dissociative symptoms associated with PTSD.	DSP-1 (Baseline (Outcome)	DSP-I
Evaluate the effect of adverse childhood experiences on PTSD treatment outcome as a covariate.	Preparatory Session 3 & Safety review, (Baseline), and (Outcome)	ACE CAPS-5
Characterization of PTSD severity with a descriptive time course plot.	Preparatory Session 3 & Safety review, , Integrative Session 1.4, and (Outcome)	PCL-5

Objectives	Assessment Window	Endpoints
Assess changes in severity of dissociative symptoms associated with PTSD treatment outcome.	CAPS-5 T1 (Baseline) and CAPS-5 T2 (Outcome)	DSP-I
Assess changes in group cohesion.	Preparatory Session 3 & Safety review, Integrative Session 1.4, Integrative Session 2.4, and Study Termination	GQ
Assess changes in depression symptoms.	Preparatory Session 3 & Safety review and Study Termination	BDI-II
Assess changes in attachment dynamics.	Preparatory Session 3 & Safety review and Study Termination	ECR-S
Assess changes in positive outcomes following trauma.	Preparatory Session 3 & Safety review and Study Termination	PTGI
Assess changes in perceived social support.	Preparatory Session 3 & Safety review and Study Termination	SPS
Assess changes in self-compassion.	Preparatory Session 3 & Safety review and Study Termination	SCS
Assess changes in health economics.	Preparatory Session 3 & Safety review and Study Termination	CSI
Assess changes in quality of life.	Preparatory Session 3 & Safety review and Study Termination	EQ-5D-5L
Assess changes in workplace productivity.	Preparatory Session 3 & Safety review and Study Termination	HPQSF

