Overall Design

This Phase 2, open-label, non-randomized, 3-cohort study assesses the feasibility and safety of MDMA-assisted group therapy for the treatment of PTSD in veterans. The study will be conducted in up to N=18 participants, recruited in three cohorts of six participants and receive therapy sessions throughout their participation in these groups.

For each participant, the study will consist of:

- **Screening Period and Enrollment:** phone screen, informed consent, eligibility assessment, and enrollment of eligible participants.
- **Preparatory Period:** initiation of medication tapering, Preparatory Sessions, and baseline assessments.
- **Treatment Period:** two Experimental Sessions, and four Integrative Sessions following each Experimental Sessions.
- **Follow-up Period and Study Termination:** Primary Outcome assessment and Study Termination visit.

After the Screening Period and Enrollment, , eligible participants will begin a ~4-week Preparatory Period. Participants will attend four, 90-minute, non-drug, Preparatory Sessions,

including three group sessions and one individual session.. Following the Preparatory Period, participants will begin an ~8-week Treatment Period comprised of two Experimental Sessions, each followed by four Integrative Sessions.

MDMA will be administered twice during the Treatment Period: one Individual Session and one Group Session. The Experimental Sessions will last ~8 hours. Four 90-minute Integration Sessions, each one week apart, will follow the Individual Experimental Session. The first Integration Session will be Individual, occurring the morning following Experimental Session 1, and the other three will be Group Integration Sessions. Finally, four Group Integration Sessions, each a week apart, will follow the Group Experimental Session. Integrative Session 2.1 will take place the morning after Experimental Session 2. A study termination visit will be conducted at the end of the study.

Number of Participants and Study Duration

Approximately 60 participants will sign an ICF and be screened to achieve up to 18 participants (in 3 cohorts of up to 6) enrolled to study intervention.

Study details include:

- The study duration following initial screening will be up to 20 weeks.
- The treatment period duration will be up to approximately 10 weeks.
- The visit frequency will be approximately weekly.

Data Monitoring/Other Committee

A Data Monitoring Committee (DMC) will not be used for this open-label study.

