8.2 Preparatory Period

Medication tapering will be initiated following enrollment, in collaboration with the prescribing physician, as applicable. Participants will undergo four Preparatory Sessions lasting approximately 90 minutes with the therapy team prior to the first Experimental Session. Adherence criteria for Preparatory Sessions should be followed per the Treatment Manual. The Preparatory Period will last 3-4 weeks, depending on duration of medication tapering. There must be at least 48 hours between Preparatory Sessions. The minimum time to complete the Preparatory Period is 3 weeks. In these visits, the therapy team will work with the participant to prepare for MDMA-assisted therapy, begin building therapeutic alliance, and promote a safe set and setting for confronting trauma-related memories, emotions, and thoughts.

Table 5: Preparatory Sessions

Visit	Individual or Group	Visit Timing
Preparatory Session 1	Group	~1 week (3 to 14 days) after Enrollment
Preparatory Session 2	Group	~1 week (3 to 14 days) after Preparatory Session 1
Preparatory Session 3	Individual	After Preparatory Session 1, but before (Baseline); Preparatory Session 2 and Preparatory Session 3 order may differ; post Taper
Baseline CAPS-5 (T1)	Individual	After Preparatory Session 3, but before Preparatory Session 4
Preparatory Session 4	Group	~3 weeks (17 to 28 days) after Preparatory Session 1; 1 to 14 days before Experimental Session 1

8.2.1 Group Preparatory Sessions 1, 2, and 5

Group Preparatory Sessions during the Preparatory Period will focus on psychoeducation about PTSD, building safety for the therapeutic relationship, developing the therapeutic alliance, and preparing participants for the first Experimental Session. Telephone calls may be scheduled between visits if indicated for tapering, safety, or any further questions about medical history.

At each 90-minute Preparatory Session, the therapy team or other qualified site staff will:

- Inquire about any possible changes in health to ensure the participant continues to meet all eligibility requirements. Record AEs as described in [Section 8.7: Adverse Events, Serious Adverse Events, and Other Safety Reporting](#).
- Inquire about concomitant medication use and adherence.
- Confirm that medication tapering is ongoing or complete, as appropriate.
- If medication tapering is ongoing at Preparatory Session 2, site team to schedule a phone call after tapering and stabilization are complete.

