8.8.5 Medical Resource Utilization and Health Economics

For all participants throughout the study, the investigator and study site personnel will collect data about health care resource utilization associated with medical encounters.

The data collected will:

- Include the reasons and duration of hospitalizations and emergency room visits.
- Exclude procedures, tests, and encounters mandated by the protocol.

The sponsor may use the collected data to conduct economic analyses.

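### The 6-month CSI recall at Study Termination reaches back before the first CSI on every scheduled path, so the termination report mixes pre-baseline with on-study service use

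*Protocol*

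**What the plan says.** The objectives table in Protocol section 1.1 lists the CSI as the endpoint for change in health economics, with two time points: "Preparatory Session 3 & Safety review and Study Termination".

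Section 8.5.4.7 describes the instrument and says "The validated assessment period is 3 months". It then departs from that openly: "This protocol will utilize a modified version of the CSI in which all services are recalled for 6 months". It gives two reasons. One is that a longer period is more likely to catch a rare hospital stay. The other is that "This reference window would also better allow a pre-study/post-study comparison with the schedule of assessments".

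On timing, section 1.1 says "The study duration following initial screening will be up to 20 weeks". The visit windows are in sections 8.2 to 8.4. Nothing in the protocol shortens the recall at termination, asks for the dates of CSI services, or removes services already reported at Preparatory Session 3.

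**The concern.** A pre/post comparison is easiest to read when the post window holds only time after the pre assessment. Here the look-back is about 26 weeks and the study after initial screening is stated as up to 20. If the termination window always includes time from before the first CSI, then the termination score is not a measure of on-study service use, although section 8.5.4.7 presents the window as suited to a pre-study/post-study comparison.

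At stake is how the health-economics result is read. The recall period is fixed when the form is filled in. Without service dates, no later analysis can separate pre-baseline from on-study use.

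**Working it through.** **Inputs: interval D from Preparatory Session 3 to Study Termination, in days**

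- Preparatory 3 to Preparatory 4: 2 to 26. The minimum comes from "There must be at least 48 hours between Preparatory Sessions". The maximum is 28 − 2, from Table 5: "3 weeks (17 to 28 days) after Preparatory Session 1; 1 to 14 days before Experimental Session 1".
- Preparatory 4 to Experimental Session 1: 1 to 14 (same row of Table 5).
- Experimental Session 1 to 2: 21 to 35, nominal 28 (Table 6).
- Experimental Session 2 to Integrative Session 2.4: 17 to 28, nominal 21 (Table 7).
- Integrative Session 2.4 to Outcome: 14 to 42, nominal 28 (section 8.4.1).
- Outcome to Study Termination: 0 to 9, nominal 7 (section 8.4.3).

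The protocol gives no nominal day for Preparatory Session 3. I assume 14 days before Experimental Session 1.

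**Interval**

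- Shortest: 2 + 1 + 21 + 17 + 14 + 0 = 55.
- Nominal: 14 + 28 + 21 + 28 + 7 = 98. If Preparatory Session 3 falls a week earlier, 105.
- Longest: 26 + 14 + 35 + 28 + 42 + 9 = 154.

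**The protocol's own duration.** Nominal spacing from Enrollment is 7 + 21 + 7 + 28 + 21 + 28 + 7 = 119 days (17 weeks), consistent with up to 20 weeks. With every window at its maximum it is 14 + 28 + 14 + 35 + 28 + 42 + 9 = 170 days (24.3 weeks), which exceeds 20. The 20 weeks is therefore a rounded bound without a derivation, and I show it as a separate case (140 days).

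**Overlap.** With 6 months taken as 182 days, overlap = 182 − D.

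| Case | D | Overlap | Share of 182 | D/182 |
|---|---|---|---|---|
| Shortest windows | 55 | 127 | 70% | 30% |
| Nominal | 98 | 84 | 46% | 54% |
| 20-week bound | 140 | 42 | 23% | 77% |
| Longest windows | 154 | 28 | 15% | 85% |

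Section 1.1 also allows a treatment period of about 10 weeks. Replacing 35 + 28 with 70 gives D = 161, and 21 days (12%) still overlap.

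**What the change score measures.** Put Preparatory Session 3 at day 0. The first report covers days −182 to 0, and the termination report covers D − 182 to D. Services in the shared stretch cancel on subtraction if they are recalled consistently. What remains is use in the D days after Preparatory Session 3 minus use in the first D days of the baseline window. At D = 98 that is days 0 to 98 against days −182 to −84, and the latest 84 baseline days drop out.

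With a constant rate r0 before day 0 and r1 after it:

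- expected raw difference = D × (r1 − r0);
- difference between two separate 6-month windows = 182 × (r1 − r0);
- ratio = D/182, the last column above.

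The same rate change gives a raw difference 154/55 = 2.8 times as large on the longest schedule as on the shortest.

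**Illustration with assumed rates.** Use falls from 1.0 to 0.5 visits per month. Two separate 6-month windows would show 6.0 and 3.0. At D = 98 days (about 3.2 months) the termination report shows 6.0 − 3.2 × 0.5 = 4.4. The change is −1.6 instead of −3.0, and the percent change is −27% (1.6/6.0) instead of −50%. A person whose only visit fell in the overlap counts as a user at both time points.

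**Would a 3-month recall help?** A window of W days at both visits has expected difference min(D, W) × (r1 − r0). With W = 91:

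- D = 55: 55 with either window; 91 − 55 = 36 days still overlap.
- D = 98: 91 against 98 with 6 months.
- D = 154: 91 against 154, and 154 − 91 = 63 on-study days are not covered.

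The 3-month recall recovers no signal in the raw difference.

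**The case against.** A reader might infer that the change in CSI is biased toward no change by construction, or that correlation through shared events spoils it. The documents do not support that. Section 9.3.3 analyses exploratory outcomes like the primary one, as change from baseline. In a raw difference the shared services cancel, leaving two non-overlapping periods of equal length D, so the sign is not distorted. The 54% is a loss only against two separate 6-month windows, which a study of this length cannot supply. Baseline and follow-up scores are correlated in any pre/post design.

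A reader might also infer that the validated 3-month recall should be restored. The departure is disclosed and argued for. Going back to 3 months would not enlarge the raw difference, could leave on-study days uncovered, and would lose pre-study inpatient history. Section 8.8.5 does not replace that history, because it collects utilization only during the study.

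Nor does every termination report necessarily count a service twice. The same calendar time is covered twice, but a service is repeated only if one was used then. Section 8.7.11 lets Experimental Sessions be delayed, which could take an individual past 6 months. Early withdrawal shortens the interval and increases the overlap.

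All of that stands. What remains is the reading of the termination score, any-use proportions and percent change, a raw change whose scale varies between participants, and a baseline comparison that drops its most recent part.

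**Conclusion.** The point holds as a minor improvement. On every planned path the termination CSI covers 28 to 127 days (about 84 nominally) of time before Preparatory Session 3 that the first CSI already covered. The finding does not depend on whether the visit windows or the 20-week duration is used. For the termination report, the claim that 6 months better serves a pre-study/post-study comparison fails: the days beyond D add nothing about on-study use.

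The 54% (30% to 85%) applies to a mean change read as a 6-month change. It assumes a constant rate that steps exactly at Preparatory Session 3, and the central value also assumes that session falls about 14 days before Experimental Session 1. The cancellation in the raw difference assumes consistent recall at both visits.

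The CSI is exploratory, the study enrolls up to 18 participants, and section 9.1 plans no formal testing. No primary, secondary or safety conclusion depends on it.

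**What to change.** Keep the 6-month recall at Preparatory Session 3. Change the termination instruction to ask for services used since Preparatory Session 3, giving the participant that date. Analyse both as rates per 30 days: baseline count × 30/182, and termination count × 30/D with D taken from the actual visit dates. This removes the overlap at any spacing, uses the whole baseline window, and makes the termination figure a measure of on-study use. In section 8.5.4.7, limit the rationale for 6 months to the baseline report.

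The cost is one instruction on the form. The termination recall length then varies between participants and is not validated, although the 6-month recall is not the validated one either. Fewer rare inpatient events will fall in the termination window. Section 8.8.5 partly covers this, since the data collected throughout the study will "Include the reasons and duration of hospitalizations and emergency room visits". A 3-month recall at both visits is a trade-off and is not needed.
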